All bleeding events will be adjudicated by a blinded, independent adjudication committee as major bleeding, CRNM bleeding, or minor bleeding. These endpoints are consistent with those recommended by the International Society on Thrombosis and Haemostasis for pediatric clinical trials in venous thromboembolism.

Secondary Endpoints:

Efficacy:

[figure not shown]
- 1) Non-fatal asymptomatic DVT
- 2) Non-fatal symptomatic DVT
- 3) Non-fatal PE
- 4) CVST
- 5) VTE-related-death

Safety:

- a) Composite of major and CRNM bleeding (CRNMB). CRNM bleeding is defined as bleeding that satisfies one or both of the following:
 - i. overt bleeding for which blood product is administered and not directly attributable to the subject's underlying medical condition and
 - ii. bleeding that requires medical or surgical intervention to restore hemostasis, other than in an operating room

Pharmacokinetics and Anti-FXa Activity

- a) Apixaban pharmacokinetics using a population pharmacokinetic (PPK) approach
- b) Anti-FXa activity

Populations for Analyses

Enrolled Population:

The Enrolled Subjects population consists of all subjects who signed informed consent.

Randomized /Intent-To-Treat (ITT) Population

The Randomized/Intent-to-Treat (ITT) population consists of all subjects who were randomized to a treatment, regardless of whether they received study drug or not. Except as noted otherwise, the Randomized/ITT Population will be used for the evaluation of efficacy.

Modified Intent-To-Treat (mITT) Population

The mITT population includes randomized subjects who have either an adjudicated event making up the primary efficacy endpoint or evaluable end of study imaging evaluations, including ultrasound and echocardiogram.

Evaluable Population

The Evaluable population will include the Randomized/ITT population except those subjects with relevant protocol deviations expected to affect the primary efficacy endpoint.

Safety Population

The safety population includes all randomized subjects since there is no intervention on top of standard care in the control arm and will be used for the evaluation of safety.

Pharmacokinetic Measures:

PK/PD samples will be taken in subjects receiving apixaban. Pre-dose and post dose concentrations of apixaban will either be measured on the same day if feasible (eg, in-patients) or on separate days (eg, out-patients). For example, the pre-dose may be taken on Day 8 ± 5 and the post-dose may be taken on Day 15 ± 5 . [REDACTED]

A PPK model will be developed using plasma concentration versus time data. Model-derived population and individual PK parameters (eg, CL/F, Vc/F, KA) will be used to estimate C_{max}, C_{min}, and AUC(TAU) in each subject. Modeling results will be reported separately.

Anti-FXa Activity Measures:

Observed pre-dose and post-dose anti-FXa activity will either be measured on the same day if feasible (eg, in-patients) or on separate days (eg, out-patients). For example the pre-dose on the Day 8 visit and the post-dose anti-FXa activity on Day 15 visit or another day. [REDACTED]

A PPK-PD model will be developed using plasma concentration and measured Anti-FXa activity versus time data. Model-derived population and individual parameters (eg, slope of anti-FXa activity vs apixaban concentration relationship) will be used to estimate maximum and minimum Anti-FXa activity in each subject. Modeling results will be reported separately.

Analyses: For primary efficacy endpoint and primary safety endpoint, statistics including event rate, 95% confidence interval (CI) for event rate, relative risk, 95% CI for relative risk and p-value will be displayed.

For other endpoints, descriptive statistics including single event rate, 95% confidence interval (CI) for single event rate, relative risk and 95% CI for relative risk will be displayed.

To construct p-values, the Cochran-Mantel-Haenszel test stratified by age groups of < 10 and \geq 10 years old will be used at the one-sided $\alpha = 0.025$ level.

To construct descriptive statistics:

[figure not shown]

- The 95% CI for the relative risk will be computed based on the Cochran-Mantel-Haenszel's method stratified by age groups of < 10 years and \geq 10 years.
- Construction of CIs for event rates will be based on the Agresti Coull's method

The analyses on all the efficacy endpoints will be based on the Randomized/ITT population.

[figure not shown]

[figure not shown]
Listings of observed PK and Anti-FXa data will be provided by Visit and age-group as appropriate.

Analyses related to the PK, PK-PD relationship, and exposure-response relationships will be described in a separate analysis plan and the results reported separate from the Clinical Study Report (CSR).

TABLE OF CONTENTS

TITLE PAGE	1
DOCUMENT HISTORY	3
OVERALL RATIONALE FOR REVISED PROTOCOL 05:	7
SUMMARY OF KEY CHANGES FOR REVISED PROTOCOL 05	7
SYNOPSIS	10
TABLE OF CONTENTS	21
1 INTRODUCTION	25
	
1.2 Dose Selection	29
1.3 Research Hypothesis	31

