Sample Size Determination: With a total of approximately 500 randomized subjects allocated with 1:1 ratio to the systemic thromboprophylaxis with apixaban (intervention) or no systemic anticoagulant prophylaxis (control) groups, there is more than 80% power to demonstrate superiority at a one-sided 0.025 level, assuming the true event rates of primary endpoint (composite of non-fatal asymptomatic and symptomatic DVT, pulmonary embolism (PE), and CVST; and VTE-related-death) are 17% and 8.5% in the control and the apixaban groups, respectively.

Sample size estimation is based on Pearson's chi-square test.

Additionally, there is more than 80% power to demonstrate superiority at a one-sided 0.025 level, assuming the true event rates are 20% and 10% in the control and the apixaban groups, respectively with analyses that assume that 20% of the subjects will be excluded from the primary analysis due to either early dropout without end-of-treatment imaging evaluation or non-evaluable end-of-treatment imaging measurement in the calculation

Randomization will be stratified by age groups as < 10 years or ≥ 10 to < 18 years, to reflect the major peaks of disease prevalence and risk stratification criteria for acute lymphoblastic leukemia (ALL) in children.

Primary Endpoints:

Efficacy:

The primary efficacy endpoint is a composite of non-fatal DVT (including asymptomatic and symptomatic), PE, and CVST; and VTE-related-death objectively confirmed by independent adjudication.

All components of the primary efficacy endpoint will be adjudicated by a blinded, independent adjudication committee.

Safety:

The primary safety endpoint will be adjudicated major bleeding which is defined as bleeding satisfies one or more of the following criteria: (i) fatal bleeding; (ii) clinically overt bleeding associated with a decrease in hemoglobin of at least 20 g/L (ie, 2 g/dL) in a 24-hour period; (iii) bleeding that is retroperitoneal, pulmonary, intracranial, or otherwise involves the CNS; and/or (iv) bleeding that requires surgical intervention in an operating suite, including interventional radiology. Of note, the major bleeding will not be considered as part of the primary endpoint for the purpose of the European application, but will be assessed as part of the safety profile of apixaban.

Prophylactic transfusions without overt bleeding and without a decrease in hemoglobin of at least 20 g/L (ie, 2 g/dL) in a 24 - hour period are not considered bleeding events.

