7.5.1 Primary Efficacy Analysis

The primary objective is compare the effect of prophylactic oral or enteric apixaban versus no administration of systemic prophylactic anticoagulant during induction chemotherapy, on the composite endpoint of adjudicated non-fatal asymptomatic and symptomatic DVT, pulmonary embolism (PE), and CVST; and VTE-related-death during intended treatment period.

To conclude superiority of apixaban versus standard care on the primary efficacy endpoint during intended treatment period, the upper bound of the two-sided 95% CI for the relative risk (p_a/p_e) must be less than 1. This condition corresponds to a test of hypothesis $H_0: p_a = p_e$ against the alternative $H_a: p_a < p_e$ using the Mantel-Haenszel test stratified by age group (<10 years or ≥ 10 to <18 years) performed at the one-sided $\alpha = 0.025$ level. Here p_a and p_e represent the proportions of subjects with primary efficacy endpoints in the apixaban and standard care groups, respectively.

Two-sided 95% CI for the relative risk (p_a/p_e) will be reported for the primary efficacy endpoint. The p-value associated with the superiority test will also be reported.

The primary efficacy analyses will be performed based on the randomized/ITT population. Subjects with no symptomatic event and no ultrasound or echocardiogram assessment will be counted as not having an event.

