7.5.1.1 Sensitivity Analyses for Primary Efficacy Endpoint

In order to assess the robustness of the effectiveness of apixaban relative to standard care, the following sensitivity analyses will be performed for the primary efficacy endpoint:

[figure not shown]
- An analysis will be performed using the mITT Population.

- An analysis will be performed for all randomized subjects with missing primary endpoint or non-evaluable imaging data to be assessed via multiple imputation using 1000 repetitions, with imputation of events for patients with missing data in both treatment groups based on the event rate observed from the corresponding stratum in the standard-of-care arm
- If results from the primary efficacy analysis show a significant difference between treatment groups, then a “tipping point” analysis will be performed with a non-stratified analysis. In each analysis, subjects with missing data in the standard-of-care arm will be assumed to be event-free, while progressively more subjects with missing data in the apixaban arm will be assigned with an event, up to the limit of the number of subjects with missing data in the apixaban arm. The number of subjects in the apixaban arm imputed with event that would change the result from significant to non-significant would be noted.
- An analysis will be performed based on the Evaluable Population, if at least 10% of subjects have a relevant protocol deviation.

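### Inclusion in the mITT population depends on the outcome, so its event rates run modestly high and its relative risk shifts if missing scans differ by arm; a two-part estimate should be added beside it

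*Protocol*

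**What the plan says.** The Protocol (Synopsis and 8.2) and SAP 6.3 define the mITT population as "randomized subjects who have either an adjudicated event making up the primary efficacy endpoint or evaluable end of study imaging evaluations", the imaging to include ultrasound and echocardiogram.

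SAP 7.5.1.1 lists it among four sensitivity analyses of the primary endpoint: "An analysis will be performed using the mITT Population". The others are multiple imputation at the control arm's stratum rate, a tipping-point analysis, and an Evaluable Population analysis that is run only if at least 10% of subjects have a relevant deviation.

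The primary analysis is ITT. SAP 7.5.1 handles missing scans thus: "Subjects with no symptomatic event and no ultrasound or echocardiogram assessment will be counted as not having an event".

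Clinically suspected events are imaged when suspected, and CVST is not screened for (Protocol Synopsis and 5.1). Some events are therefore found without the scheduled scan by design. The documents do not give that share, nor the missing-scan rate by arm. The only figure is an overall allowance in the sample-size text: "20% of the subjects will be excluded from the primary analysis due to either early dropout without end-of-treatment imaging evaluation" or because the imaging is non-evaluable.

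**The concern.** The two routes into the mITT population are not symmetric. A detected event is enough on its own, whereas a child without one needs evaluable scans. Missing scans therefore remove event-free children from the denominator but never remove a clinically found event. If both imaging modalities are required, partial imaging has the same effect: a positive ultrasound without an echocardiogram keeps the child in, and a negative one does not.

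The size of the distortion grows with the share of missing scans, so it does not cancel when the arms differ. A difference is plausible. The trial is open-label, apixaban scans are timed from stopping drug, and control scans are timed from Day 29. The direction cannot be predicted from the documents.

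At stake is how the mITT result is read. It is the one planned analysis that appears to estimate each arm's rate from that arm's own observed scans. No listed analysis does this without bias when scans are missing at random at unequal rates:

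- ITT scores unscanned children as event-free, and the Evaluable analysis removes only deviators.
- Multiple imputation draws apixaban's missing outcomes at the control rate, which dilutes a real effect.
- The tipping point is a one-directional stress test.

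**Working it through.** **Plan's own figures.** Inputs: "approximately 500 randomized subjects allocated with 1:1 ratio", one-sided 0.025, rates that "are 17% and 8.5% in the control and the apixaban groups, respectively", and a second scenario "assuming the true event rates are 20% and 10% in the control and the apixaban groups, respectively" after 20% exclusion (500 × 0.8 / 2 = 200 per arm). With the uncorrected Pearson formula,

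power = Φ{[(p1 − p2)√n − 1.96√(2p̄(1 − p̄))] / √(p1(1 − p1) + p2(1 − p2))}.

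- 250 per arm, 17% vs 8.5%: (1.344 − 1.96 × 0.4717)/0.4678 = 0.897, power 81.5%.
- 200 per arm, 20% vs 10%: (1.414 − 1.96 × 0.5050)/0.5 = 0.849, power 80.2%.

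Both agree with the statement that "there is more than 80% power to demonstrate superiority at a one-sided 0.025 level".

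**Expected mITT rate.** Let p be the true event rate, f the share of events found other than by the scheduled scan, and m the share of the remaining children with no evaluable scan, missing at random. Then

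mITT rate = [fp + (1 − m)(1 − f)p] / [fp + (1 − m)(1 − fp)].

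f is assumed to be 10–50%. If f = 0 the rate is exactly p, so scan-found events alone cause no bias.

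**Equal missingness, m = 20%.**

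- p = 17%, f = 10%: (0.017 + 0.8 × 0.153)/(0.017 + 0.8 × 0.983) = 0.1394/0.8034 = 17.4%.
- p = 17%, f = 50%: 0.153/0.817 = 18.7%.
- p = 8.5%, f = 10%: 0.0697/0.8017 = 8.7%.
- p = 8.5%, f = 50%: 0.0765/0.8085 = 9.5%.

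The relative risk is 0.50–0.51 against a true 0.50, and the one-sided error stays at 2.5%.

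**Unequal missingness, no drug effect** (17% in both arms, 250 per arm, simulated, unstratified tests). The by-arm missing rates are assumptions. The entries are one-sided rejection rates for f = 10 / 30 / 50%; repeated runs agree to about 0.1 percentage point.

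| Missing, control / apixaban | mITT | ITT | Both significant | Two-part |
|---|---|---|---|---|
| 25% / 10% | 3.1 / 4.4 / 6.0% | 0.4 to 1.0% | 0.4 / 0.6 / 1.0% | 2.4–2.5% |
| 10% / 25% | 2.0 / 1.4 / 0.9% | 11.0 / 8.1 / 5.9% | 2.0 / 1.4 / 0.9% | 2.6–2.7% |

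In the first row at f = 50%, the expected mITT rates are 0.14875/0.77125 = 19.3% (control) and 0.1615/0.9085 = 17.8% (apixaban). That is a relative risk of 0.92 where the truth is 1. With a smaller gap, 22% vs 18% missing, the mITT error is 2.7–3.2%.

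**Why the two-part estimate works.** Take S = fp over all randomized, and A = (1 − f)p/(1 − fp) among scanned children with no earlier event. Then S + (1 − S)A = fp + (1 − f)p = p, whatever m is. Under 17% vs 8.5% with 20% missing in both arms, its power matches that of crude mITT (0.74–0.78).

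**If scans are not missing at random.** Suppose unscanned children without a clinical event have k times the silent-clot rate of scanned children. At 17% and m = 20%, the true rate is 0.1394 + 0.0306k for f = 10% and 0.153 + 0.017k for f = 50%. The mITT rate becomes too low once k exceeds (0.1735 − 0.1394)/0.0306 ≈ 1.1 or (0.1873 − 0.153)/0.017 ≈ 2.0 respectively.

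**The case against.** The strongest reply is that nothing in the trial turns on mITT. SAP 7.5.1 concludes superiority only from the stratified ITT test, and mITT is one of four robustness checks with no stated priority. That stands: an mITT rejection rate above 2.5% is not a type I error problem for the trial.

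A reader might also infer that, because mITT is biased, agreement between ITT and mITT says nothing about robustness. The plan's own rules imply the opposite. ITT counts unscanned children as event-free, so more missing scans lower an arm's ITT rate and raise its mITT rate. In the simulations both tests were falsely significant together less than 2.5% of the time in every setting tried. Where ITT is the inflated test (apixaban missing more scans), mITT holds joint significance to about 2% or less.

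It is also fair that multiple imputation and the tipping point do not use mITT membership and lean against apixaban. They are useful stress tests, but neither gives a missing-at-random estimate of each arm's rate.

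Finally, the larger figures need a 15-point gap in missing scans, and the documents give no split by arm. The two-part estimate itself also assumes that scans are missing at random. Both points are accepted. They limit the size and the claim, but do not remove the asymmetry in the definition.

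**Conclusion.** The definition makes inclusion depend on the outcome. If scans are missing at random within arm and f is above zero, both mITT rates are modestly too high: 0.4 to 1.7 points on 17%, and 0.2 to 1.0 point on 8.5%, at 20% missing and f of 10–50%. With equal missingness the relative risk and error rate are essentially unaffected. With 25% vs 10% missing, the one-sided error of the mITT test moves to about 3–6%, or about 1–2% with the arms reversed. The share f, the by-arm missing rates and missing at random are all assumptions.

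Two stronger readings do not hold. The mITT population does not keep every child with an event: the definition requires an adjudicated one, so an unscanned child with a silent clot is dropped. Nor are the rates always too high, since the direction changes if unscanned children have enough extra silent clots.

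The primary conclusion is untouched. The harm is confined to the reported mITT rates and relative risk, and to any ITT–mITT disagreement, which cannot be interpreted cleanly. This is a worthwhile, inexpensive improvement.

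**What to change.** In SAP 7.5.1.1, keep the mITT analysis and add, as the missing-at-random sensitivity analysis, a two-part estimate for each arm and age stratum:

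- S = adjudicated events found other than by the scheduled end-of-study scan, divided by all randomized.
- A = events found by the scheduled scan, divided by children with no such earlier event and an evaluable scan.
- Rate = S + (1 − S)A.

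Combine strata with Mantel-Haenszel weights and use a delta-method interval. State that the estimate assumes scans are missing at random within arm and stratum, and that detection route is assigned from the adjudicated event date and the scheduled-scan date. Say how a child with only one of the two imaging modalities counts, with the same rule for positive and negative findings. Report the share of evaluable scans by arm beside the result.

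The cost is one SAP paragraph and a little programming. It needs only event adjudications and scan dates already collected. The downside is an estimate slightly less simple to explain than a crude proportion.

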1 INTRODUCTION

[figure not shown]

[figure not shown]

[figure not shown]

1.2 Dose Selection

Based on PK simulations performed with this model a dosing scheme has been selected for the age cohort to be enrolled (1 to < 18 years):

Dose Selection

With the introduction of 0.5-mg tablets, the dosing paradigm of apixaban changed from mg/kg dosing to a fixed-dose, body weight-tiered regimen, as outlined in [Table 1.2-2](#). The fixed-dose, body weight-tiered regimen will use apixaban doses in increments of 0.5-mg according to the appropriate weight range, regardless of apixaban formulations (i.e. oral solution or 0.5-mg tablets). The modelling and simulation results, support the current dosing recommendation of a fixed-dose body weight-tiered regimen for pediatric subjects aged 3 months to < 18 years. The age range for enrollment in this study will remain age 1 year to < 18 years. Study medication will be administered in accordance with the instructions provided. While subjects ≥ 5 years may be administered either 2.5-mg, 0.5-mg tablets or oral solution apixaban, use of 2.5 mg or 0.5 mg tablets is encouraged.

Subjects < 5 years and <35 kg may be administered 0.5-mg tablets only. Switching formulations during the course of the study is not encouraged but is allowed.

The previously unopened 9 to < 12 kg weight tier will be redistributed into the 2 adjacent weight tiers and dosed as follows: 6 to < 10.5 kg patients will be dosed 0.5 mg and 10.5 to <18 kg patients will be dosed 1 mg. The original proposal was for patients with body weight in the tier of 9 to < 12 kg to receive a 0.75-mg dose. The redistributed regimen provides similar exposures to the 0.75-mg dose originally listed in the protocol.

Subjects 1 to < 18 years of age will be administered apixaban twice daily by mouth or via a NGT or GT according to weight range as per below Table 1.2-2 during approximately 28 days of induction chemotherapy including asparaginase.

Table 1.2-2: Apixaban Doses for Ages 1-18 Years of Age

Weight range	Dose
≥ 35 kg	2.5 mg twice daily
<35 to 25 kg	2 mg twice daily
<25 to 18 kg	1.5 mg twice daily
<18 to 10.5 kg	1 mg twice daily
<10.5 to 6 kg	0.5 mg twice daily

The previously communicated dosing for the body weight tier of 9 to < 12 kg has been redistributed into a 6 to < 10.5 kg weight tier and a 10.5 to < 18 kg weight tier.

Apixaban will be administered during approximately 28 days of induction chemotherapy including asparaginase.

1.3 Research Hypothesis

Administration of prophylactic apixaban, orally or via a nasogastric or gastric tube (NGT, GT), during induction chemotherapy will reduce the risk of venous thromboembolism (symptomatic + asymptomatic), compared to no systemic anticoagulant prophylaxis, during induction chemotherapy in children with newly diagnosed ALL or lymphoblastic lymphoma (T or B cell) treated with asparaginase.

[figure not shown]
1.4 Objectives(s)

[figure not shown]
1.4.1 Primary Objectives

[figure not shown]
- To compare the effect of prophylactic oral or enteric apixaban versus no systemic anticoagulant during ~28 days of induction chemotherapy including asparaginase on the composite endpoint of adjudicated non-fatal deep vein thromboses (DVT, including symptomatic and asymptomatic), pulmonary embolism (PE), and CVST; and VTE-related-death.
- To assess the effect of prophylactic oral or enteric apixaban versus no systemic anticoagulant during ~28 days of induction chemotherapy including asparaginase on adjudicated major bleeding events.

[figure not shown]
1.4.2 Secondary Objectives

[figure not shown]
- To assess the effect of prophylactic apixaban versus no systemic anticoagulant during ~28 days of induction chemotherapy including asparaginase on single adjudicated endpoints of non-fatal DVT (including symptomatic and asymptomatic), PE, and CVST; and VTE-related-death.
- To assess the effect of prophylactic apixaban versus no systemic anticoagulant during ~28 days of induction chemotherapy including asparaginase on the composite endpoint of adjudicated major and clinically relevant non-major bleeding (CRNMB) events.

[figure not shown]

[figure not shown]

2 ETHICAL CONSIDERATIONS

2.1 Good Clinical Practice

This study will be conducted in accordance with Good Clinical Practice (GCP), as defined by the International Conference on Harmonisation (ICH) and in accordance with the ethical principles underlying European Union Directive 2001/20/EC and the United States Code of Federal

Regulations, Title 21, Part 50 (21CFR50). The study will be conducted in compliance with the protocol. The protocol and any amendments and the subject informed consent will receive Institutional Review Board/Independent Ethics Committee (IRB/IEC) approval/favorable opinion prior to initiation of the study. All potential serious breaches must be reported to BMS immediately. A serious breach is a breach of the conditions and principles of GCP in connection with the study or the protocol, which is likely to affect, to a significant degree, the safety or physical or mental integrity of the subjects of the study or the scientific value of the study.

Study personnel involved in conducting this study will be qualified by education, training, and experience to perform their respective task(s). This study will not use the services of study personnel where sanctions have been invoked or where there has been scientific misconduct or fraud (eg, loss of medical licensure, debarment).

